6.2.4 Secondary Outcome

The time to event variables in the secondary outcomes will be analyzed similarly with the primary outcome.

As 1-4 vessels were generally measured in each subject, the vein graft patency at 5 years after CABG is a categorical data measured repeatedly in subjects. The number and the percentage of the grafts in Fitzgibbon grade B/O will be summarized by the group in previous DACAB study. GEE (Generalized Estimating Equations) was used to compare the subjects' saphenous vein graft patency rate among groups.

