4.2 Secondary Outcome

- MACE-5, defined as a composite of all-cause death, myocardial infarction, stroke, coronary revascularization and hospitalization for unstable angina. The outcome measure is the time to the first occurrence of MACE-5 event from randomization to the last visit;
- MACE-3, defined as a composite of cardiovascular death, myocardial infarction and stroke. The outcome measure is the time to the first occurrence of MACE-3 event from randomization to the last visit;
- All-cause death. The outcome measure is the time to the first occurrence of all-cause death from randomization to the last visit;
- Cardiovascular death. The outcome measure is the time to the first occurrence of cardiovascular death from randomization to the last visit;
- Myocardial infarction. The outcome measure is the time to the first myocardial infarction from randomization to the last visit;
- Stroke. The outcome measure is the time to the first stroke from randomization to the last visit;
- Coronary revascularization. The outcome measure is the time to the first coronary revascularization from randomization to the last visit.;

- Hospitalization for unstable angina. The outcome measure is the time to the first hospitalization for unstable angina from randomization to the last visit;
- Graft failure/vein graft failure at the last visit (Fitzgibbon Grade B/O assessed by CCTA or CAG). The outcome measure is the incidence of graft failure/vein graft failure.

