4.3 Evaluation and Calculation of Endpoints

The primary outcome is the time to the first occurrence of any MACE-4, which is a composite of all-cause death, myocardial infarction, stroke, and coronary revascularization and measured in days since the date of randomization. Subjects who had not experienced any major adverse clinical events from randomization to the last visit will be right-censored. For those subjects who lost to follow-up at 5-year visit, the date of the last contact and the most updated clinical outcomes available in medical record or other source will be used in primary analysis. If there's no major adverse clinical events recorded for those subjects who lost to follow-up at 5-year visit, then these subjects will be right-censored at the date of their last contact. The survival curves will be estimated using Kaplan-Meier method.

The secondary outcomes (time to event) will be analyzed similarly with the primary observational endpoint.

Graft failure after CABG is in accordance with Fitzgibbon classification criteria by using MSCTA or CAG, there were a total of 3 categories, grade A, B and O, where grade A accounted for graft patency (no lesions), and grade B/O accounted for the graft failure.

5. Subject Selection Criteria

All the subjects enrolled in the DACAB trial.

6. Statistical Analysis

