6.2.3 Primary Outcome

Kaplan-Meier will be used to estimate survival curves, and calculate the incidence of major adverse clinical events-4 (MACE4) for each year during the follow-up period. Log-rank test will be used to compare the differences between survival curves. COX regression model will be used to estimate hazard ratios and its 95% confidence intervals.

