7.1.3 Secondary Outcomes

Table 9 Occurrence of secondary outcomes during the follow-up (FAS)

Indicator/Group	Overall occurrence of the event	Event rate during follow-up				
		12 months	24 months	36 months	48 months	60 months
MACE5						
A	*** (***)	**%	**%	**%	**%	**%
T+A	*** (***)	**%	**%	**%	**%	**%
T	*** (***)	**%	**%	**%	**%	**%
MACE3						
A	*** (***)	**%	**%	**%	**%	**%
T+A	*** (***)	**%	**%	**%	**%	**%
T	*** (***)	**%	**%	**%	**%	**%
All-cause death						
A	*** (***)	**%	**%	**%	**%	**%
T+A	*** (***)	**%	**%	**%	**%	**%
T	*** (***)	**%	**%	**%	**%	**%
Cardiovascular death						
A	*** (***)	**%	**%	**%	**%	**%
T+A	*** (***)	**%	**%	**%	**%	**%
T	*** (***)	**%	**%	**%	**%	**%

Event rate during follow-up

Indicator/Group	Overall occurrence of the event	12 months	24 months	36 months	48 months	60 months
Myocardial infarction						
A	*** (***)	**%	**%	**%	**%	**%
T+A	*** (***)	**%	**%	**%	**%	**%
T	*** (***)	**%	**%	**%	**%	**%
Stroke						
A	*** (***)	**%	**%	**%	**%	**%
T+A	*** (***)	**%	**%	**%	**%	**%
T	*** (***)	**%	**%	**%	**%	**%
Coronary revascularization						
A	*** (***)	**%	**%	**%	**%	**%
T+A	*** (***)	**%	**%	**%	**%	**%
T	*** (***)	**%	**%	**%	**%	**%
Hospitalization for unstable angina						
A	*** (***)	**%	**%	**%	**%	**%
T+A	*** (***)	**%	**%	**%	**%	**%
T	*** (***)	**%	**%	**%	**%	**%

Note: Overall occurrence of the event includes all the events during the follow-up period, KM was used to estimate the event rates in different visit.

Table 10 Survival analysis for secondary outcomes during follow-up (FAS)

Indicator/Group	HR(95% CI)	Logrank P
MACE5		
T+A VS. A	*** (***, ***)	0. ****
T VS. A	*** (***, ***)	0. ****
T+A VS. T	*** (***, ***)	0. ****
MACE3		
T+A VS. A	*** (***, ***)	0. ****
T VS. A	*** (***, ***)	0. ****
T+A VS. T	*** (***, ***)	0. ****
All-cause death		
T+A VS. A	*** (***, ***)	0. ****
T VS. A	*** (***, ***)	0. ****
T+A VS. T	*** (***, ***)	0. ****
Cardiovascular death		
T+A VS. A	*** (***, ***)	0. ****
T VS. A	*** (***, ***)	0. ****
T+A VS. T	*** (***, ***)	0. ****
Myocardial infarction		
T+A VS. A	*** (***, ***)	0. ****
T VS. A	*** (***, ***)	0. ****
T+A VS. T	*** (***, ***)	0. ****
Stroke		

Indicator/Group	HR(95% CI)	Logrank P
T+A VS. A	*** (***,***)	0. ****
T VS. A	*** (***,***)	0. ****
T+A VS. T	*** (***,***)	0. ****
 Coronary revascularization		
T+A VS. A	*** (***,***)	0. ****
T VS. A	*** (***,***)	0. ****
T+A VS. T	*** (***,***)	0. ****

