7.2.2 Major clinical events

Table 28 Occurrence of clinical events during the follow-up (grouped by total grafts failure at 1 year)

Indicator/Group	Overall occurrence of the event	Event rate 2-5 years during follow-up			
		24 months	36 months	48 months	60 months
MACE4					
Patency	*** (***)	**%	**%	**%	**%
Failure	*** (***)	**%	**%	**%	**%
MACE5					
Patency	*** (***)	**%	**%	**%	**%
Failure	*** (***)	**%	**%	**%	**%
MACE3					
Patency	*** (***)	**%	**%	**%	**%
Failure	*** (***)	**%	**%	**%	**%
All-cause death					
Patency	*** (***)	**%	**%	**%	**%
Failure	*** (***)	**%	**%	**%	**%
Cardiovascular death					
Patency	*** (***)	**%	**%	**%	**%
Failure	*** (***)	**%	**%	**%	**%

Event rate 2-5 years during follow-up

Indicator/Group	Overall occurrence of the event	24 months	36 months	48 months	60 months
Myocardial infarction					
Patency	*** (***)	**%	**%	**%	**%
Failure	*** (***)	**%	**%	**%	**%
Non-silent MI					
Patency	*** (***)	**%	**%	**%	**%
Failure	*** (***)	**%	**%	**%	**%
Stroke					
Patency	*** (***)	**%	**%	**%	**%
Failure	*** (***)	**%	**%	**%	**%
Coronary revascularization					
Patency	*** (***)	**%	**%	**%	**%
Failure	*** (***)	**%	**%	**%	**%

Table 29 Survival analysis for clinical events (grouped by total grafts failure at 1 year)

Indicator/Group	HR(95% CI)	Adjusted P
MACE4		
Failure VS. Patency	*** (***, ***)	0. ****
MACE5		
Failure VS. Patency	*** (***, ***)	0. ****
MACE3		
Failure VS. Patency	*** (***, ***)	0. ****
All-cause death		
Failure VS. Patency	*** (***, ***)	0. ****
Cardiovascular death		
Failure VS. Patency	*** (***, ***)	0. ****
Myocardial infarction		
Failure VS. Patency	*** (***, ***)	0. ****
Non-silent MI		
Failure VS. Patency	*** (***, ***)	0. ****
Stroke		
Failure VS. Patency	*** (***, ***)	0. ****
Coronary revascularization		
Failure VS. Patency	*** (***, ***)	0. ****

Table 30 Occurrence of clinical events (grouped by saphenous vein grafts failure at 1 year)

Note: same as table 28, grouped only according to saphenous vein grafts failure at 1 year.

Table 31 Survival analysis for clinical events (grouped by saphenous vein grafts failure at 1 year)

Note: same as table 29, grouped only according to saphenous vein grafts failure at 1 year.

Table 32 Grafts patency during 1-5 years follow-up

Indicator	Overall	Patency (A)	Failure (O/B)	Adjusted P
Total grafts at 1 year				0.***
N(missing)	*** (***)	*** (***)	*** (***)	

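### Kaplan-Meier yearly incidence of six secondary outcomes takes no account of competing death, so the Table 9 rates and Figures 4 and 6-10 run high, probably by a small amount

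*SAP*

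**What the plan says.** SAP 6.2.3 uses Kaplan-Meier to "calculate the incidence of major adverse clinical events-4 (MACE4) for each year during the follow-up period", with log-rank tests and a Cox model for the comparisons. SAP 6.2.4 carries this over: "The time to event variables in the secondary outcomes will be analyzed similarly with the primary outcome". Protocol 9.2.4 says the same.

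The Table 9 shell (SAP 7.1.3) lists MACE-5, MACE-3, all-cause death, cardiovascular death, myocardial infarction, stroke, coronary revascularization and unstable-angina hospitalization, with event rates at 12, 24, 36, 48 and 60 months. Its note names the estimator: "KM was used to estimate the event rates in different visit". Figures 3 to 10 are the matching Kaplan-Meier curves.

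The censoring rule in SAP 4.3 is written for the primary outcome: "Subjects who had not experienced any major adverse clinical events from randomization to the last visit will be right-censored". The same section extends the approach: "The secondary outcomes (time to event) will be analyzed similarly with the primary observational endpoint". Subjects lost to follow-up without an event are censored at last contact. Neither document says how a subject is handled who dies without having had the outcome under analysis, and neither mentions competing risks or a cumulative incidence function.

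**The concern.** Kaplan-Meier suits MACE-4, MACE-5 and all-cause death because every death is an event in them. The other six outcomes differ. SAP 4.2 describes myocardial infarction thus: "The outcome measure is the time to the first myocardial infarction from randomization to the last visit". A subject who dies without an infarction can no longer have one, and the same holds for stroke, revascularization and unstable-angina hospitalization. MACE-3 is "MACE-3, defined as a composite of cardiovascular death, myocardial infarction and stroke", so a non-cardiovascular death ends the risk without counting as an event. Cardiovascular death is in the same position.

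The secondary objective is to compare incidence among the three regimens. Protocol 9.2.3 describes the primary rate as that of subjects with a first event within 1 to 5 years, and Protocol 9.2.4 carries the approach to the secondary outcomes. That is a proportion of the actual subjects. If competing deaths are censored, one minus Kaplan-Meier instead estimates the risk in a hypothetical population in which nobody dies of the competing cause. At stake is the accuracy of the yearly percentages in Table 9 and of the curves in Figures 4 and 6-10.

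**Working it through.** **Stated figure.** 168 + 166 + 166 = 500 randomized. Subtracting the 5 deaths before the 12-month visit gives the 495 in Protocol 9.3. The documents give no five-year event rate, no five-year death rate and no power calculation.

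**Inputs**
- Deaths in year 1: 5/500 = 1.0% (SAP 6.3; Protocol 9.3).
- Five-year mortality is an assumption. Holding 1.0% a year constant gives 1 − 0.99^5 = 4.9%, taken as about 5%. The range examined is 2% to 20%.
- Five-year Kaplan-Meier event rates of 3%, 10% and 20% are illustrative.

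**Formulas**, with constant cause-specific hazards h1 (event) and h2 (competing death) over 5 years:
- One minus Kaplan-Meier: K = 1 − exp(−5·h1).
- Competing mortality: D = 1 − exp(−5·h2).
- Cumulative incidence (the Aalen-Johansen target): C = h1/(h1 + h2) × [1 − exp(−5(h1 + h2))].

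**Worked case, K = 10% and D = 5%**
- h1 = −ln(0.90)/5 = 0.02107; h2 = −ln(0.95)/5 = 0.01026.
- h1/(h1 + h2) = 0.6726; 1 − exp(−5(h1 + h2)) = 1 − 0.90 × 0.95 = 0.145.
- C = 0.6726 × 0.145 = 9.75%.
- Overstatement: 10 − 9.75 = 0.25 points; 10/9.75 − 1 = about 2.5% relative.

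A simulation of 1,000,000 subjects gave 9.79%, within its sampling error (standard error about 0.03 points).

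**Range**

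| Assumed five-year competing mortality | Overstatement at K = 3% (points) | At K = 10% (points) | At K = 20% (points) | Relative |
|---|---|---|---|---|
| 2% | 0.03 | 0.10 | 0.19 | about 1% |
| 5% | 0.08 | 0.25 | 0.49 | about 2.5% |
| 10% | 0.15 | 0.50 | 0.98 | about 5% |
| 15% | 0.23 | 0.76 | 1.48 | about 8% |
| 20% | 0.31 | 1.02 | 2.00 | about 11% |

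**By arm.** Extrapolating the year-1 deaths in each arm (A 3/166, T+A 2/168, T 0/166) gives five-year mortality of 8.7%, 5.8% and 0%. A Kaplan-Meier rate of 10% then corresponds to a cumulative incidence of 9.57%, 9.71% and 10.0%. This rests on five deaths, so it shows only that the bias need not be equal across arms.

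**Cardiovascular death and MACE-3.** Only non-cardiovascular deaths compete here, and Protocol 5.3.2 counts undetermined deaths as cardiovascular. Their D is therefore below total mortality, and the overstatement is smaller than for the other four outcomes.

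**The case against.** The strongest reply is that this hardly matters.

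- **Size.** At 4.9% five-year mortality the overstatement on a 10% rate is 0.24 points. The binomial standard error with 166 subjects is √(0.10 × 0.90/166) = 2.3 points, so the bias is about a tenth of one standard error. This stands, and it limits the weight of the point.
- **Inference.** The between-arm comparisons are in Table 10. Log-rank tests and Cox hazard ratios that censor competing deaths are valid for cause-specific hazards. This also stands. A reader might infer that the secondary treatment comparisons are wrong; they are not.
- **Wording.** Censoring at a competing death is nowhere written out. True, but it is what Kaplan-Meier does under the only censoring rule given.

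A stronger reading is also tempting: that the rates for subjects with and without one-year graft failure (Tables 28 and 30) would show a false difference caused by mortality alone. The documents do not support it, for three reasons.

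1. Those tables name no estimator. The Kaplan-Meier note is under Tables 5, 7 and 9, and SAP 6.2.9 assigns the cohort comparison to an adjusted GLM.
2. The size depends on mortality figures that the documents do not give. With 5% against 15% mortality and a true incidence of 15% in both cohorts, Kaplan-Meier would show 15.4% against 16.2%. But the study in Protocol Table 1 of angiograms up to 18 months after surgery reports an adjusted hazard ratio for death of 1.04 (0.71 to 1.52) with vein graft failure. Other rows of that table do report worse survival.
3. The false gap depends on holding cumulative incidence equal. If the cause-specific hazards are equal instead (Kaplan-Meier 15% in both), cumulative incidence is 14.6% against 13.9%, a gap of about 0.75 points the other way.

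**Conclusion.** The point holds for six outcomes, in Table 9 and Figures 4 and 6-10. The direction is certain whenever a competing death occurs. The size is probably small: about 0.25 points on a 10% rate at about 5% five-year competing mortality, and it reaches 1 point on a 10% rate only when that mortality is near 20%. These sizes assume constant hazards and mortality extrapolated from year 1, since the documents contain no later deaths. It is a descriptive bias in secondary results. It leaves the primary analysis and the validity of the hazard ratios untouched, and the documents do not establish it for the graft-failure cohorts. It is worth correcting because the direction of error is known, six of the eight outcomes in Table 9 are affected, and the correction uses data already collected.

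**What to change.** In SAP 6.2.4, Table 9 and its note, and Figures 4 and 6-10:

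- Estimate the 12- to 60-month incidence of the six outcomes with the Aalen-Johansen cumulative incidence function.
- Take death from any cause as the competing event for myocardial infarction, stroke, coronary revascularization and unstable-angina hospitalization. Take non-cardiovascular death for cardiovascular death and MACE-3, with undetermined deaths classed as in Protocol 5.3.2.
- Keep Kaplan-Meier for MACE-4, MACE-5 and all-cause death.
- Keep the log-rank and Cox results in Table 10, labelled as cause-specific for the six outcomes. Gray's test or a Fine-Gray model could be added as a sensitivity analysis.
- State which estimator Tables 28 and 30 use. If it is Kaplan-Meier, make the same change for the affected outcomes there.

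The cost is a few lines of SAP text and a small program change. Reported rates will be slightly lower. Because cumulative incidence itself depends on mortality, it should be read alongside the cause-specific hazard ratios and all-cause death.

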There are 500 patients were enrolled from July 2014 through November 2015 and follow-up was completed in January 2017, 168 patients in the T+A group, 166 in T group and 166 in A group. The results showed that the 1-year SVG patency rate (primary endpoint) of T+A group was 88.7% (432/487, T+A vs A, p=0.0006), the T group was 82.8% (371/485, T vs A, p=0.0962), and the A group was 76.5% (404/488). The incidence of MACE during 1 year of follow-up was 1.8% in T+A group, 2.4% in T group, and 5.4% in A group. The DACAB trial demonstrated that compared with aspirin monotherapy, the combination of ticagrelor and aspirin significantly improved 1-year SVG patency after CABG. Meanwhile, the combination of ticagrelor and aspirin therapy or ticagrelor monotherapy showed a favor trend with reducing the MACEs compared with aspirin monotherapy.

Would the observed differences in SVG patency at 1 year post CAGB translate into long-term clinical benefit? This remain to be a great interest to follow up these patients. Therefore, in present study, we intend to collect and analyze the long-term data in patients who were enrolled and survived in DACAB trial. We would observe the clinical outcomes of these subjects at 5-year post-CABG.

2. Study Objectives

- Primary Objective**

The primary objective is to compare the incidence of major adverse clinical events-4 (MACE-4, a composite of all-cause death, myocardial infarction, stroke, and coronary revascularization) among 3 randomized regimens in previous DACAB trial in the extended five-year follow-up after CABG.

- Secondary Objectives**

The secondary objectives are to compare the incidence of MACE-5 (a composite of all-cause death, myocardial infarction, stroke, coronary revascularization and hospitalization for unstable angina); MACE-3 (a composite of cardiovascular death, myocardial infarction and stroke); all-cause death; cardiovascular death; myocardial infarction; stroke; coronary revascularization; hospitalization for unstable angina and graft failure among 3 randomized regimens in previous DACAB trial in the five-year follow-up after CABG.

- Exploratory Objectives**

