6.2 Methods of Statistical Analyses

6.2.1 General Method of Analysis

Counts and percentages for discrete variables, and mean, SD, maximum, minimum, median, 25th percentiles and 75th percentiles for continuous

variables will be used to summarize data.

The missing data will be assumed missing at random, no imputation will be applied unless specified otherwise.

A 2-sided level of significance of .05 will be applied to all statistical analyses unless specified otherwise. Statistical analyses will be performed using SAS 9.4.

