6.3 Sample Size

A total of 500 subjects were randomized in DACAB study (ticagrelor + aspirin, 168; ticagrelor alone, 166; aspirin alone, 166). There were 5 subjects died before 12-month visit, of these, 2 died in ticagrelor + aspirin group, and 3 died in aspirin alone group.

7. Results of Statistical Analysis

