	(***% to ***%)	(***% to ***%)	(***% to ***%)	(***% to ***%)	(0.** to 0.**)		(***% to ***%)	(0.** to 0.**)		(***% to ***%)	(0.** to 0.**)	
Patency rate 1 month-1 year after surgery	***%	***%	***%	***%	0.**	0.***	***%	0.**	0.***	***%	0.**	0.***
	(***% to ***%)	(***% to ***%)	(***% to ***%)	(***% to ***%)	(0.** to 0.**)		(***% to ***%)	(0.** to 0.**)		(***% to ***%)	(0.** to 0.**)	
Patency rate 1-5 years after surgery	***%	***%	***%	***%	0.**	0.***	***%	0.**	0.***	***%	0.**	0.***
	(***% to ***%)	(***% to ***%)	(***% to ***%)	(***% to ***%)	(0.** to 0.**)		(***% to ***%)	(0.** to 0.**)		(***% to ***%)	(0.** to 0.**)	
Saphenous vein graft	S	***	***	***								

Patency rate(95%CI)			A+T VS. A			T VS. A			A+T VS. T		
A+T		T	Rate difference (95%CI)	RR(95%CI)	p	Rate difference (95%CI)	RR(95%CI)	p	Rate difference (95%CI)	RR(95%CI)	p
A											
Patency rate 1-5 years after surgery	***%	***%	***%	***%	0.**	***%	0.**	0.***	***%	0.**	0.***
	(***% to ***%)	(***% to ***%)	(***% to ***%)	(***% to ***%)	(0.** to 0.**) 0.***	(***% to ***%)	(0.** to 0.**) 0.***	(***% to ***%)	(***% to ***%)	(0.** to 0.**) 0.***	

Note: rate difference, RR and p value were estimated by GEE.

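### Table 10 prints 24 secondary log-rank P values, each judged at two-sided .05, with nothing marking them as nominal

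*SAP*

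**What the plan says.** The secondary objectives are comparative. SAP section 2 opens them with "The secondary objectives are to compare the incidence of MACE-5" and goes on to the other outcomes among the three randomized regimens. Protocol 2.2 does the same.

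The SAP then sets the method and the level:

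- SAP 6.2.3, for the primary: "Log-rank test will be used to compare the differences between survival curves". Cox regression supplies the hazard ratios.
- SAP 6.2.4 carries this over: "The time to event variables in the secondary outcomes will be analyzed similarly with the primary outcome".
- SAP 6.2.1 sets the threshold: "A 2-sided level of significance of .05 will be applied to all statistical analyses unless specified otherwise". Nothing different is specified for secondary outcomes.

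Table 10 in SAP 7.1.3 lays out the result. For MACE-5, MACE-3, all-cause death, cardiovascular death, myocardial infarction, stroke, coronary revascularization and hospitalization for unstable angina, it has one hazard ratio and one log-rank P value for each of T+A vs A, T vs A and T+A vs T. Table 13 adds P values for graft patency in the same three contrasts, with the footnote "Note: rate difference, RR and p value were estimated by GEE".

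Protocol 9.2.3 and 9.2.4 name only Kaplan-Meier estimates and graft summaries, and 9.2.1 leaves detailed methods to the SAP. The tests therefore come from the SAP.

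**The concern.** Read literally, the plan gives every secondary contrast the same standing as the primary one: a P value below .05 is significant. Nothing makes a secondary finding depend on MACE-4, ranks the outcomes or contrasts, or adjusts for their number. If MACE-4 showed no difference, a single P<.05 on one component in one contrast would still meet the SAP's criterion. Because subjects are analysed by randomized group, it would be read as a 5-year effect of the regimen. With 24 such chances, an isolated result of this kind is weak evidence, and the plan does not warn the reader of that.

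**Working it through.** The documents state no familywise error rate, power or event target, so there is no figure of the plan's own to reproduce.

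**Inputs from the documents**
- Level per test: two-sided .05 (SAP 6.2.1), so reject if |Z| > 1.96.
- Outcomes: 8 time-to-event secondaries (SAP 4.2, items other than graft failure).
- Contrasts per outcome: 3 (Table 10).
- Arms: A 166, T+A 168, T 166 (SAP 6.3).
- Follow-up: 5 years ± 3 months (protocol 3.1).

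**Search for a control.** Neither document has a gate, a sequence, a global test, an alpha adjustment or a nominal label for these outcomes. The term exploratory is applied only to the graft-failure cohorts and the subgroups (protocol 2.3; SAP 2 and 6.2.10). The adjusted P columns in Tables 29 and 32 belong to the graft-failure cohort tables, where SAP 6.2.9 plans adjustment for confounders. They are not a multiplicity adjustment of Table 10.

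**Count and expectation.** 8 × 3 = 24 tests. With no true difference, the expected number with P<.05 is 24 × .05 = 1.2, whatever the correlation between tests.

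**Chance of at least one**

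1. Reference, all 24 independent: 1 − .95^24 = 0.708. This is too high, because contrasts share arms and outcomes overlap.
2. Shared arms, one outcome: three pairwise tests give 0.122. Eight independent outcomes of that kind give 1 − (1 − 0.122)^8 ≈ 0.65.
3. Shared arms and correlated outcomes. For outcome k and arm a, take y = [√ρ·c_a + √(1−ρ)·u_ka]/√n_a, with c and u standard normal, and Z = (y_i − y_j)/√(1/n_i + 1/n_j). With 200,000 null runs for each ρ:

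| Correlation ρ (assumed) | P(at least one of 24) |
|---|---|
| 0 | 0.648 |
| 0.2 | 0.618 |
| 0.5 | 0.507 |
| 0.8 | 0.340 |
| 0.9 | 0.266 |

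4. Patient-level simulation: 500 patients, exponential event times with no arm effect, death censoring non-fatal events, MACE-5 and MACE-3 built from their components, linked events (for example, infarction leading to revascularization), and pairwise log-rank tests. There were 1,500 runs per scenario, so the Monte Carlo SE at 0.5 is √(.25/1500) = 0.013. All event rates are assumptions. The middle set of 5-year risks is cardiovascular death 4%, other death 3%, infarction 4%, stroke 8%, revascularization 5% and unstable angina 10%.
   - Low, middle and high rates, each with frailty variance 0, 1 and 3: 0.51 to 0.57.
   - Middle rates with strong links between events: 0.53.
   - A deliberately extreme overlap of outcomes: 0.46.

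**Scale check.** Bonferroni over the 24 tests (.05/24 = 0.0021 each) brings the simulated chance down to 0.025–0.033. This shows that the excess comes from the number of tests and not from a poor log-rank approximation.

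**The case against.** The best defence is that the plan already ranks these outcomes below one named primary, describes the study as non-interventional and observational (protocol 3.2), and nowhere says that an isolated secondary P<.05 will support a claim. The .05 in SAP 6.2.1 is a level per test, and unadjusted secondary P values are common. Much of this stands: formal familywise control over the secondaries is not something the SAP offered and then failed to deliver. What remains is that the SAP attaches a significance level to these P values and never says they are nominal.

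A reader might infer more than the documents support in three places:

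- *That a false positive appears half the time as a fact about this trial.* The figure depends on assumed correlation and event rates. At correlation 0.9 it is 27%.
- *That every sensible subset runs at five or more times .05.* For T+A vs A alone (8 tests) the simulations give 24–29%, and the normal model gives 25% at correlation 0.5 and 16% at 0.8. Moreover, a family rate and a per-test level are different quantities.
- *That the first-year rows of Table 13 merely repeat published DACAB results.* The background sections report 1-year saphenous vein patency by arm. The first-year rows visible in Table 13 are for total grafts, and no comparison by arm for those windows is reported in either document. Protocol 5.2 also plans re-assessment of original images.

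**Conclusion.** The point holds for the 24 tests of Table 10. As written, the plan lets any one of them be called significant at .05 without reference to MACE-4. If the regimens are equal on all eight outcomes, about one spurious result is expected, and the chance of at least one is near one half, with a range of about one third to two thirds for correlations from 0.8 down to 0. The expected count of 1.2 needs only the complete null and tests that hold their level. The probability also needs the assumed correlations or event rates. If some outcomes truly differ, both figures apply only to the remaining true nulls and are smaller.

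The primary analysis is not affected. Table 13 extends the same open rule to graft patency, but it is not counted in the figures here. The three unadjusted MACE-4 contrasts are a separate matter.

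**What to change.** Amend SAP 6.2.1 to read: *The .05 significance level applies to the primary outcome; P values for secondary outcomes are nominal.*

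Add to SAP 6.2.4 and to the footnotes of Tables 10 and 13: *Secondary outcomes are reported as HR (or patency difference/RR) with unadjusted 95% CI; P values are nominal, not adjusted for multiplicity, and no claim of statistical significance is made from them.*

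Use nominal or supportive, not exploratory. Protocol 2.2–2.3 and SAP 2 keep secondary and exploratory objectives as separate tiers, and relabelling in 6.2.4 alone would contradict them.

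The cost is wording and footnotes, with no new data or analysis. The one loss is that an isolated secondary P<.05 can no longer be called significant.
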